Appendix 2: Duplex ultrasonography

Both legs will be fully investigated ([Coleridge Smith, 2006](#)).

Venous Duplex ultrasonography

Venous obstruction will be assessed using the duplex ultrasonography performed with a superficial probe (7 to 13 Megahertz or MHz), on a participant in supine position, to explore the veins listed below (obstruction list). Vein compression, retrograde flow in deep and superficial veins using compression of the calf muscles, echography B mode, pulsed wave and colour Doppler will be used.

For venous valve incompetence, the participant will be examined in standing position. Reflux will be search on the veins listed below with compression of the calf or valsalva manoeuvre for veins above knee, and with compression on the foot for veins below knee. Reflux will be considered if retrograde flow lasted > 0.5 second for superficial veins, anterior and posterior tibial veins, peroneal veins, perforator veins, and if retrograde flow lasted > 1 second for common femoral vein, femoral vein, and popliteal vein.

Please, tick the appropriate boxes:		Right/Left leg	
		Not present	Present
Reflux	Great Saphenous Vein above knee	(0) 	(1) 
	Great Saphenous Vein below knee	(0) 	(1) 
	Small Saphenous Vein	(0) 	(1) 
	Non saphenous superficial veins	(0) 	(1) 
	Gastrocnenial, soleal veins	(0) 	(1) 
	Tibial anterior vein	(0) 	(1) 
	Tibial posterior vein	(0) 	(1) 
	Peroneal vein	(0) 	(1) 
	Popliteal vein	(0) 	(1) 
	Femoral vein	(0) 	(1) 
	Common femoral vein	(0) 	(1) 
Please, tick the appropriate boxes:		Right/Left leg	
Obstruction	Not present		Present
	Great Saphenous Vein above knee	(0) 	(1) 
	Great Saphenous Vein below knee	(0) 	(1) 
	Small saphenous vein	(0) 	(1) 
	Non saphenous superficial veins	(0) 	(1) 
	Gastrocnenial, soleal veins	(0) 	(1) 
	Tibial anterior vein	(0) 	(1) 
	Tibial posterior vein	(0) 	(1) 
	Peroneal vein	(0) 	(1) 
	Popliteal vein	(0) 	(1) 
	Femoral vein	(0) 	(1) 
	Deep femoral vein	(0) 	(1) 
	Common femoral vein	(0) 	(1) 
	Pelvic veins*	(0) 	(1) 
	Internal iliac vein*	(0) 	(1) 
	External iliac vein*	(0) 	(1) 
	Common iliac vein*	(0) 	(1) 
Inferior vena cava*	(0) 	(1) 	

*If probe for this assessment is available (e.g. convex probe from 3.5 to 5MHz)

Arterial Duplex ultrasonography

Duplex ultrasonography of the artery system will also be performed in the leg affected by the reference ulcer in order to check for arteriopathy from iliac to tibial arteries.

Leg affected by the reference ulcer				
Methods**				
	Method 1 (Planimetry)	Method 2 (Velocity)	Method 3 (Flow type / Waveform)	
Arteriopathy	Common iliac artery*	% stenosis 	cm/s 	Flow type (0-5) 
	Internal iliac artery*	% stenosis 	cm/s 	Flow type (0-5) 
	External iliac artery*	% stenosis 	cm/s 	Flow type (0-5) 
	Common femoral artery	% stenosis 	cm/s 	Flow type (0-5) 
	Internal femoral artery	% stenosis 	cm/s 	Flow type (0-5) 
	External femoral artery	% stenosis 	cm/s 	Flow type (0-5) 
	Popliteal artery	% stenosis 	cm/s 	Flow type (0-5) 
	Tibial anterior artery	% stenosis 	cm/s 	Flow type (0-5) 
	Tibial posterior artery	% stenosis 	cm/s 	Flow type (0-5) 
	Peroneal artery	% stenosis 	cm/s 	Flow type (0-5) 
	Dorsal pedal artery	% stenosis 	cm/s 	Flow type (0-5) 

*If probe for this assessment is available (e.g. convex probe from 3.5 to 5MHz)

** For either Method 1 (planimetry) or Method 2 (velocity measurement) or Method 3 (flow type), please fill in all boxes under the heading of that method for which results are available. If results by Methods 2 and 3 are available, please fill them both.

For information: flow type (waveform) of the arterial curve

0 = no flow; 1 = trickle flow; 2 = damped monophasic; 3 = monophasic; 4 = biphasic; 5 = triphasic

Appendix 3: Venous Leg Ulcer

A leg ulcer is defined as a non-healing ulcer that fails to heal after a period of 6 weeks. A venous leg ulcer will be defined as full-thickness defect of skin, most frequently in ankle region, that fails to heal spontaneously and is sustained by documented CVD. Typical localization for venous ulcers: the gaiter area – from just below the ankle or malleolus up to, but not including the knee flexural crease.

For the study purposes the largest existing venous leg ulcer fitting the selection criteria in a participant becomes the Reference Ulcer (RU). All selection/inclusion criteria referring to ulcer characteristics take into account RU.

Appendix 4: Revised CEAP Classification

The CEAP classification (Clinical-Etiology-Anatomy-Pathophysiology) was adopted Worldwide to facilitate meaningful communication about CVD and serve as a basis for more scientific analysis of management alternatives.

Clinical classification

- C0: no visible or palpable signs of venous disease
- C1: telangiectasies or reticular veins
- C2: varicose veins
- C3: edema
- C4a: pigmentation or eczema
- C4b: lipodermatosclerosis or atrophie blanche
- C5: healed venous ulcer
- C6: active venous ulcer

Even if the patient will be C6, other classification from C1 to C5 will have to be defined (e.g. a patient could be C1, C3 and C6).

Each clinical class is further characterized by a subscript for the presence of symptoms (s, symptomatic) or absence of symptoms (a, asymptomatic), for example, C2a or C5s.

Symptoms include heaviness, pain, aching, tightness, skin irritation, muscle cramps, and other complaints attributable to venous dysfunction.

Etiologic classification

- Ec: congenital
- Ep: primary
- Es: secondary (postthrombotic)
- En: no venous cause identified

(Only Ep, Es and En will have to be defined)

Anatomic classification

- As: superficial veins
- Ap: perforator veins
- Ad: deep veins
- An: no venous location identified

(Only As, Ad and An will have to be defined)

Pathophysiologic classification (basic)

- Pr: reflux
- Po: obstruction
- Pr,o: reflux and obstruction
- Pn: no venous pathophysiology identifiable

Advanced CEAP: Same as basic CEAP, with addition that any of 18 named venous segments can be used as locators for venous pathology

Superficial veins (will have to be defined)

- Telangiectasies or reticular veins
- Great saphenous vein above knee
- Great saphenous vein below knee
- Small saphenous vein
- Nonsaphenous veins

Deep veins (will have to be defined)

- Inferior vena cava
- Common iliac vein
- Internal iliac vein
- External iliac vein
- Pelvic: gonadal, broad ligament veins, other
- Common femoral vein
- Deep femoral vein
- Femoral vein
- Popliteal vein
- Crural: anterior tibial, posterior tibial, peroneal veins
(all paired)
- Muscular: gastrocnemial, soleal veins, other

Perforating veins: (will not have to be defined)

- Thigh
- Calf

Appendix 5: Ankle Brachial Pressure Index

Continuous wave Doppler (CWD) is used to perform the assessment of the Ankle Brachial Pressure Index (ABPI) with a probe of 8 MHz (5 MHz for obese patient). The main objective is to determine resting ankle systolic pressure and resting brachial systolic pressure (as an approximation of central pressure).

Systolic blood pressure will be measured after 10 minutes of rest on both arms in sitting or supine position and on each foot on the following 2 locations: posterior tibial, and anterior tibial. Each measurement will be performed twice and tables will have to be completed in a specific form (see [Appendix 12](#)).

If CWD is not available, the following procedure will be performed with the Duplex Ultra Sonography with a superficial probe (7 to 13 MHz).

Explain the procedure and reassure the patient and ensure that he/she is lying flat and is comfortable, relaxed and rested with no pressure on the proximal vessels.

1. Measure the brachial systolic blood pressure:

- Place an appropriately sized cuff around the upper arm
- Locate the brachial pulse (humeral artery) and apply ultrasound contact gel
- Angle the Doppler probe and move the probe to obtain the best signal
- Inflate the cuff until the signal is abolished then deflate the cuff slowly and record the pressure at which the signal returns being careful not to move the probe from the line of the artery (in case of duplex ultrasonography: signal returns must be associated to the systolic curve on the screen)
- Repeat the procedure for the other arm
- Use the highest of the two values to calculate the ABPI

2. Measure the ankle systolic pressure:

- Place an appropriately sized cuff around the ankle immediately above the malleoli having first protected any ulcer that may be present by dressing and cling film
- Examine the foot, locating the **anterior tibial pulse** and apply contact gel ([Figure 3](#))

Figure 3 -

- Continue as for the brachial pressure, recording this pressure in the same way

Repeat this for the **posterior tibial** ([Figure 4](#))

Figure 4 - The posterior tibial artery lies just behind the medial malleolus. Reflux can frequently be heard in the adjacent veins and this can help to locate the artery

3. ABPI calculation

- Use the highest reading obtained to calculate the ABPI for that leg (each arterial signal must be present: posterior tibial, anterior tibial, if not, occlusion must be excluded by duplex scan)
- Repeat for the other leg
- Calculate the ABPI for each leg using the formula below:

$$ABPI_l = \frac{P_l}{P_a}$$

ABPI_l = ABPI for a leg

P_l = Highest pressure obtained from the ankle vessels for that leg

P_a = Highest brachial pressure of the two arms

Causes of error in ABPI calculations

Too small cuff size at the ankle: overestimate of the ABPI.

Repeatedly inflating and deflating: inaccurate pressure reading.

Inappropriate cuff position, as the pressure recorded is the pressure at the level of the cuff and not the pressure at the site of the Doppler probe.

Bad probe: normally 8MHz when assessing superficial blood vessels (best combination of depth of tissue penetration and focus). Obese patient or oedematous legs: 5MHz probe.

Bad position of the probe: ideally 45 degrees to the skin surface with contact gel in case of CWD.

Participants will be eligible for the study if ABPI measured as above is found to be above or equal to 0.8 and below or equal to 1.3

Appendix 6: Ulcer Infection

Chronic wounds are almost always contaminated with micro-organisms and in small numbers they do not necessarily delay healing. Where infection occurs it is most commonly caused by bacteria. The criteria used to describe bacterial loading have been loosely defined by EWMA as follows:

- Contamination is the presence of bacteria with no multiplication
- Colonisation describes multiplication of bacteria with no host response
- Infection is said to be present when there is invasion of healthy tissue with a host response

Assessment of ulcer infection will be made by clinical means taking into account traditional inflammatory signs: redness, swelling, hyperthermia, pain and limited function. Additionally the following parameters should be also considered:

- Increased exudate: substantial increase in the amount of exudate, possibly with increased viscosity, change in colour, offensive odour.
- Friable granulation tissue
- Slough
- Changed odour
- Changed pain
- Stagnation in the healing process
- Serological markers of systemic infection, e.g. leucocytosis, increased CRP

For the purpose of the study, ulcer infection will be graded in 4 different grades taking into account the extent of inflammatory signs:

Grade 1: no signs or symptoms of infection

Grade 2: in subcutaneous tissue only

Grade 3: extensive erythema, infection of deeper tissue

Grade 4: systemic inflammatory response indicating severe infection

Participants with infection of Grades 2-3-4 will undergo medical management at the investigator's discretion including antibiotherapy, except local antibiotherapy on the surface of RU. Should the antibiotics be required for *more than 7 days* during the same month to control the infection the participant will be withdraw from the study.

Appendix 7: Renal Failure Classification

The Kidney Disease Outcomes Quality Initiative (K/DOQI) of the National Kidney Foundation (NKF) defines chronic kidney disease as either kidney damage or a decreased glomerular filtration rate (GFR) of less than 60 ml/min/1.73 m² for 3 or more months. Whatever the underlying etiology, the destruction of renal mass with irreversible sclerosis and loss of nephrons leads to a progressive decline in GFR. The different stages of chronic kidney disease form a continuum in time.

In 2002, K/DOQI published its classification of the stages of chronic kidney disease, as follows:

- Stage 1: Kidney damage with normal or increased GFR (>90 ml/min/1.73 m²)
- Stage 2: Mild reduction in GFR (60-89 ml/min/1.73 m²)
- Stage 3: Moderate reduction in GFR (30-59 ml/min/1.73 m²)
- Stage 4: Severe reduction in GFR (15-29 ml/min/1.73 m²)
- Stage 5: Kidney failure (GFR < 15 ml/min/1.73 m² or dialysis)

Estimation of eGFR

Estimation of eGFR will be done using the Modification of Diet in Renal Disease (MDRD) formula

For creatinine in mg/dL:

- Female patients
eGFR= [186 x Serum creatinine^{-1.154} x (Age)^{-0.203}] x 0.742 x 0.95
- Male patients
eGFR= [186 x (Serum creatinine)^{-1.154} x (Age)^{-0.203}] x 0.95

For creatinine in µmol/L:

- Female patients
eGFR= [186 x (Serum creatinine x 0.0113)^{-1.154} x (Age)^{-0.203}] x 0.742 x 0.95
- Male patients
eGFR= [186 x (Serum creatinine x 0.0113)^{-1.154} x (Age)^{-0.203}] x 0.95

The laboratory will automatically calculate estimated eGFR according to the above formulas. Participants having eGFR < 30 ml/min/1.73 m² or participants requiring dialysis are not eligible for participating in the study.

Appendix 8: Heart Failure Classification

Participant's cardiac function should be assessed prior inclusion. In case of heart failure the New York Heart Association (NYHA) functional classification system will be used. This system relates symptoms to everyday activities and the participant's quality of life.

Class	Symptoms
Class I (Mild)	No limitation of physical activity. Ordinary physical activity does not cause undue fatigue, palpitation, or dyspnea (shortness of breath).
Class II (Mild)	Slight limitation of physical activity. Comfortable at rest, but ordinary physical activity results in fatigue, palpitation, or dyspnea.
Class III (Moderate)	Marked limitation of physical activity. Comfortable at rest, but less than ordinary activity causes fatigue, palpitation, or dyspnea.
Class IV (Severe)	Unable to carry out any physical activity without discomfort. Symptoms of cardiac insufficiency at rest. If any physical activity is undertaken, discomfort is increased

Patients with heart failure class III and IV are not eligible to participate in the study.

Appendix 9: Questionnaire for Pain Assessment

Please ask the participant the following questions before cleansing and debridement and tick with an X (☒) the response(s) that is/are the most appropriate based on your impression. One or several boxe(s) can be checked as appropriate, according to the participant's response:

[figure not shown]
[figure not shown]
1. Do you feel any pain or discomfort (aching, heaviness, fatigue, soreness, burning) related to your leg ulcer?

- No
- Yes If Yes, how would you characterize the intensity of pain or discomfort since your last visit on the following scale (from 0 being no pain to 10 being the worst possible pain)?

Please ask the participant to draw a vertical line on the horizontal axis in accordance with the intensity of his pain since his/her last visit.

*In case the VAS is not properly completed, please follow the rules defined on the ruler given at the beginning of the study.

2. How would you characterize your pain or discomfort in relation with your daily activities?

- None
- Occasional pain or discomfort that does not restrict regular daily activities
- Daily pain or discomfort that interferes with, but does not prevent, regular daily activities
- Daily pain or discomfort that limits most regular daily activities

(None = 0)
(Mild = 1)
(Moderate = 2)
(Severe = 3)
(*For the investigator use)

3. Is the pain continuous/constant?

- No
- Yes

4. Is the pain mostly related with:

- Dressing change
- Debridement
- Other procedure,

Please specify which procedure(s) (for example, wearing compression stockings, etc...):

5. Is the pain or discomfort more predominant during specific periods of the day:

- Night
- Morning
- Afternoon
- Evening
- Same intensity along the whole day

6. Do you need to take medication for control of the pain associated to VLU ?

- No
- Yes

If yes, please specify (analgesic drug consumption):

- drug name: _____
- daily dose and number of intakes : _____

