At the inclusion visit (W000), these measurements will be used by the investigator to check if the RU area was in the range of inclusion criteria and if the change in the RU area between ASSE and W000 is less or equal to 20% for inclusion.

Area Change $w_0-ASSE = | \text{Reference Ulcer Area W000} - \text{Reference Ulcer Area ASSE} | / \text{RU Area ASSE}$. (Reference Ulcer Area ASSE is the one after cleansing and debridement).

Patients found to be eligible for randomisation will also have a 3D picture of the RU on the day of W000 (taken after randomisation) that will be uploaded by the investigator (or a delegated person) on the secured website to send these pictures to the central reviewer.

At W001, W002, W003, W004, W006 and W008, the investigator (or a delegated person) will upload the 3D pictures of RU on the secured website to send these pictures to the central reviewer.

In addition to the RU area measurement, the CRO in charge of the central measurement will perform volume and perimeter measurements at each visit on the 3D picture. These measures will be used for the efficacy criteria.

- Pain assessment

The questionnaire with the VAS will be provided by I.R.I.S and completed at the beginning of W000, W004 and W006 visits, before RU clinical assessment and local care of the RU. The participant will draw a vertical line on the scale to reflect his perception on the intensity of the pain since the last visit. The investigator will measure the exact distance from 0 to the line

drawn by the participant and report the corresponding measurement in millimetres in the e-CRF together with documenting the answers to all the questions.

- Reference Ulcer clinical assessment

The form for RU clinical assessment will be completed after the pain assessment and will be reported in the e-CRF at each study visit: ASSE, W000, W001, W002, W003, W004, W006 and W008.

- Analgesic drug consumption:

Analgesic intake follow-up related to VLU: will be evaluated and reported in the e-CRF at W000, W004 and W006 visits and will be addressed to patient using analgesic drug linked to VLU.

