5.2.3. Efficacy analysis

Linear advance of the wound margin

Computation of **linear advance** of the wound margin towards the wound center from baseline:

$$\bar{d} = \frac{\Delta A}{\bar{p}}$$

Where ΔA is the difference in the area ($A_{\text{visit}} - A_{\text{baseline}}$) and p the average of the wound perimeter:

$$(\bar{p} = \frac{P_{\text{visit}} + P_{\text{Baseline}}}{2})$$

Computation of **linear advance** of the wound margin towards the wound center from previous visit:

$$\bar{d} = \frac{\Delta A}{\bar{p}}$$

Where ΔA is the difference in the area ($A_{\text{visit } v} - A_{\text{visit } v-1}$) and p the average of the wound perimeter:

$$(\bar{p} = \frac{P_{\text{visit } v} + P_{\text{visit } v-1}}{2})$$

Pain intensity

Pain intensity is defined as the Visual Analog Scale (VAS) values.

In case of response “No” to the question “Does the participant feel any pain or discomfort related to his/her leg ulcer?” and the VAS value is missing this value will be imputed to zero.

Diabetic status

For efficacy analysis, a patient with $\text{HbA1c} \geq 6.5\%$ or a medical history in the following list : 1689.2 Evidences of diabetes mellitus M220 is considered as diabetic.

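### Pain question 1 has no recall window yet decides who gets a since-last-visit VAS, and a blank VAS after No becomes zero even if question 2 records pain

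*Protocol*

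**What the plan says.** Four places bear on this.

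- **Protocol Appendix 9, question 1** asks "Do you feel any pain or discomfort (aching, heaviness, fatigue, soreness, burning) related to your leg ulcer". It gives no recall period. The VAS hangs on the Yes box: "Yes If Yes, how would you characterize the intensity of pain or discomfort since your last visit on the following scale".
- **The instruction heading that form** fixes the timing ("Please ask the participant the following questions before cleansing and debridement") and gives two bases for the tick: first "the response(s) that is/are the most appropriate based on your impression", then "One or several boxe(s) can be checked as appropriate, according to the participant's response".
- **Protocol 7.2** describes the VAS with no yes/no condition. The participant draws a line "to reflect his perception on the intensity of the pain since the last visit", and the investigator enters the distance in millimetres along with the answers to every question.
- **SAP 5.2.3** defines pain intensity as the VAS value. When the answer to "Does the participant feel any pain or discomfort related to his/her leg ulcer" is No, "and the VAS value is missing this value will be imputed to zero".

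SAP 3.4.3 then describes the VAS at W000, W004 and W006, and its change from baseline to W004 and W006. No test is planned.

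**The concern.** The item that opens the gate and the scale behind it cover different periods. The form itself allows for pain that comes and goes: question 2 has a category for occasional pain, question 3 asks whether pain is constant, question 4 links it to procedures, and question 5 asks about time of day. It is completed at the start of the visit, before wound care (also note 8 to Table (4.2.2) 1). At W000, W004 and W006 participants come fasting and before the morning dose (Protocol 6.1), which suggests a morning visit. A truthful No about the present is therefore compatible with pain since the last visit.

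On this form the VAS is blank by design after a No, so the zero rule is the ordinary route and not a rare fallback. A wrong zero at W004 or W006 reads as complete relief. A wrong zero at W000 leaves no room to improve. The planned tables would not expose the conflict. SAP 3.4.3 reports the VAS and the yes/no medication item (question 6) but not questions 2 to 5, although Protocol 4.1.2 lists change in pain characteristics. The VAS is the only measure of pain intensity that the SAP analyses.

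**Working it through.** The plan gives no figure to reproduce here, so the check follows one record through the text and then sizes the effect.

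**Scoring path**

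1. Suppose a participant has had intermittent pain since the last visit, would mark 40 mm (assumed), and has none on arrival.
2. Question 1 is read as meaning now. The answer is No, the form does not lead to the VAS, and the VAS stays blank.
3. Question 2 is answered with the occasional category (coded Mild = 1). Protocol 7.2 has this entered in the e-CRF.
4. SAP 5.2.3 looks only at question 1 and the blank VAS. The value becomes 0, and question 2 is not consulted.
5. If the participant marked 40 mm at W000 and this happens at W004, the recorded change is 0 − 40 = −40 mm, where a marked VAS would have given 40 − 40 = 0. If it happens at W000 instead, the recorded change is 40 − 0 = +40 mm, again where 0 was due.

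The path breaks in two places. A participant who reads question 1 as covering recent pain answers Yes and marks the VAS. A line drawn despite a No is kept, because the zero applies only to a missing value.

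**Size (illustrative only)**

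Downward shift of an arm mean at one visit = p × m, where p is the share of the arm wrongly set to zero and m is the mean VAS those participants would have marked. The documents give neither. Assumed ranges: p from 5% to 20%, m from 10 to 40 mm, on a line taken to be 100 mm long.

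- Low end: 0.05 × 10 = 0.5 mm
- Middle: 0.10 × 20 = 2 mm
- High end: 0.20 × 40 = 8 mm

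One input is documented: SAP 1.3 reports 121 patients included, so 121 / 6 ≈ 20 per arm. One wrong zero in place of an assumed 40 mm moves an arm mean by 40 / 20 = 2 mm.

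**Which comparisons are affected**

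The error in the difference between arms A and B has size pA × mA − pB × mB. It is zero if both arms have the same p and m. If p differed by 10 percentage points at m = 20 mm, it would be 0.10 × 20 = 2 mm. The same holds for change from baseline: it is affected only if p or m differs between W000 and the later visit.

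**The case against.** The strongest reply is that question 1 never says now. The form uses the simple present for lasting states elsewhere, as in the questions on need for medication and on constant pain. Question 1 also runs straight into an intensity rating since the last visit. Asking before debridement whether pain is mostly due to debridement makes sense only if a Yes can cover pain that is absent at that moment. This stands in part: some participants will read it broadly, and the number who do not is unknown. It does not remove the mismatch, because nothing on the form tells participants which reading applies.

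Four stronger readings are tempting, and the documents do not support them.

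- A reader might infer that participants with intermittent pain *are* scored as pain-free. The text shows only that they *can* be.
- A reader might infer that the investigator's impression decides the tick. The same instruction tells the investigator to ask the participant and to tick according to the reply, and the participant draws the VAS line. The wording is contradictory, but it is not investigator scoring.
- A reader might infer a bias between arms, for instance because the drug makes pain intermittent or a visible side effect colours the tick. Nothing in the documents suggests either.
- A reader might infer that zero imputation is wrong in itself. Without it, truly pain-free patients, including healed ones, would be missing and arm means would be too high.

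It is also fair that data validation and a blind review are planned (Protocol 14.2). Whether a conflict between questions 1 and 2 would be queried cannot be seen from the documents. The medication item tabulated under SAP 3.4.3 gives a partial cross-check. Figures are missing from the form as reproduced, so its printed layout cannot be fully judged.

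**Conclusion.** The point holds as a minor one. Protocol Appendix 9 and Protocol 7.2 differ on who marks the VAS. SAP 5.2.3 contains a rule that can assign 0 against an answer on the same form. How often this would happen is unknown. The 0.5 to 8 mm range rests wholly on assumed inputs and describes one arm's mean at one visit, not a treatment difference. The rule is identical in all blinded arms, pain is a secondary objective summarised without a test, and the primary analysis of ulcer area is untouched. The case for acting is that the correction is cheap and uses items already collected.

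**What to change.** **SAP 5.2.3, settled before unblinding.** Impute a missing VAS to 0 only when question 1 is No and question 2 is None. Leave conflicting records missing, report their number by arm and visit, and show the present zero rule as a sensitivity analysis. Do not also require No at question 6 (need for pain medication): a patient whose pain is fully controlled by medication may be a true zero, and that condition would discard it.

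**Appendix 9, for any form still to be used.** Reword question 1 to ask whether ulcer-related pain or discomfort has been felt since the last visit, or have every participant mark the VAS as Protocol 7.2 describes. Replace the reference to the investigator's impression with the participant's own answer. The SAP is dated 02 March 2020 and gives 121 as the final number included, so this part probably comes too late for most of the present data.

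**Cost.** One SAP sentence, one small table and one repeated summary. The drawback is some additional missing VAS values, possibly informative. At the assumed 5% to 20% and about 20 per arm, that is at most 0.05 × 20 = 1 to 0.20 × 20 = 4 per arm and visit, which is why the present rule should stay as a sensitivity analysis. Question 2 has no recall window either, so a participant who answers both questions about the present would still be scored 0. The SAP change catches only the records that contradict themselves.
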